### 2.0 Add Department(s)

2.1 List departments associated with this study

Primary Dept?	Department Name
---------------	-----------------

No Department(s) have been attached to this form.

3.5 If applicable, please select the Administrative Assistant: (s)

Administrative Assistant Note

This role performs routine IRB submissions and has no contact with subjects, their data, records or specimens. Human Subject Protection Training is not required for this role.

### 4.0 Institutional Review Board Oversight

Version 2/23/17 (55)

4.1 Will you be requesting a deferral?

Yes  No

Will you be requesting a deferral from UW-Madison so that **UnityPoint Health - Meriter IRB** will be your IRB of record?

- **UnityPoint Health - Meriter IRB** is used for investigator initiated research performed by UW affiliates through the Meriter and UW-Madison IRB Partnership Agreement.
- Do not use this form to request UW-Madison to be the IRB of record.

Yes  No

Will you be requesting a deferral from UnityPoint Health - Meriter so that **Western IRB** will be your IRB of record?

- **Western IRB (WIRB)** is used for multi-site clinical research sponsored by pharmaceutical companies.

Yes  No

## 5.0 Research Details for UW-Madison Deferrals to UnityPoint Health - Meriter IRB

5.1 Why do you think UnityPoint Health - Meriter Institutional Review Board should be the IRB of record for your research?

**Use the Deferral Criteria Chart in the HELP Bubble over in the right panel to answer this question. Site the criteria that applies to your project.**

1. all subjects recruited, medical records used, or study activities occur at Meriter
2. Studies involving collection of data through noninvasive procedures routinely employed in clinical practice (except x-rays, microwaves, or devices not cleared/approved for marketing) that involve Meriter and UW/UWHC/UWMF patients

5.2 Will any of the following subject populations be involved? Check all that apply.

- Neonates
- Fetuses
- Prisoners
- Subjects recruited from Meriter Child and Adolescent Psychiatry Unit or Meriter Addiction Medicine
- Patients from Madison VA, including use of their records or samples obtained from them.
- Patients from UWHC, including use of their records or samples obtained from them.
- Patients from a UWMF clinic, including use of their records or samples obtained from them.
- None of the Above

5.3 Please indicate the number of subjects, samples, and/or records you plan to get from each institution.

60

Additional Comments

5.4 For each research procedure in the left column, please indicate where it will occur. Skip to the next question if these procedures do not apply to your research.

Research Procedure	Meriter	UW Hospital & Clinics	UWMF	Name of Other Institution Site	Name of Other Institution Site
Record Review		 null	 null		

Subject Recruitment	 null	 null		
Specimen Banking or Collection	 null	 null	 null	
Administration of a drug or implantation of a device that has NOT been approved by FDA.	 null	 null	 null	

5.5 Do you have additional research procedures not listed above? Add them in the table below.

Research Procedure	Meriter	UW Hospital & Clinics	UWMF Clinic	Name of Other Institution Site	Name of Other Institution Site
Non-invasive Near Infrared Spectroscopy (NIRS) monitoring					

## 6.0 Study Type

6.1 \* Study Type - Check only those that apply: iRIS will provide you with only the questions that apply to the type of research you are doing. Read the HELP Bubble in the right panel BEFORE checking a Study Type.

- General Biomedical Research
- Research on Biological Specimens
- Program Improvement - Quality Assurance
- Record Review Research
- Social/Behavioral/Educational Research - Survey, Interview, Questionnaire, Observation
- Research at Meriter when Meriter is Not Engaged - See HELP Bubble at right.
- Humanitarian Use Device
- Other

If "other" enter information below. Contact IRB Office for additional help on Study Type.

6.2 Are you doing this project to fulfill an educational requirement?

Yes  No

## 7.0 Clinical Trials Registration Requirement

7.1 \*Registration at ClinicalTrials.gov may be required in the following situations: Per FDA regulations, most studies involving the testing of a drug, biologic, or device must be registered. If publications resulting from this study will be published in a member journal of the International Committee of Medical Journal Editors (ICMJE) or in a publication that adheres to ICMJE standards, the study must be registered. Does this study need to be registered at Clinicaltrials.gov?

- Yes
- Not Applicable

7.2 If your research is listed on another public website, please provide the URL to the listing for this research.

## 8.0 Clinical Trials Registration Details

8.1 Who will register this study at ClinicalTrials.gov prior to the enrollment of the first subject?

PI- [name]

8.2 Help us verify that your protocol is registered on ClinicalTrials.gov Type in the ClinicalTrials.gov Identifier (also known as the NCT number) below.

## 9.0 Study Funding I

### 9.1 Instructions for Study Funding Sections

The IRB reviews financial relationships or interests that may adversely affect the rights and welfare of subjects. Please answer the following questions completely. You may attach additional documentation if you need to explain your answers. **SANCTIONS for Failure to Report Financial Conflicts of Interest** If the IRB determines that a Researcher has failed to report a financial conflict of interest as required, the IRB may immediately withdraw approval of the protocol and may bar the investigator from any future research at Meriter Hospital for a period of time specified by the IRB.

9.2 \*Does any of the local research staff, their immediate family, or dependents have a proprietary interest in the research, such as current or future ownership, royalties, patents, trademarks, copyright, or licensing agreement, including any agent, device, or software being evaluated as part of the research?

Yes  No

- Tell who has the interest.
- Describe the person's role in relationship to the research.
- Describe the plan to avoid conflict of interest while working on the research.

9.3 \*Is your research being funded, has it ever been funded, or do you anticipate it being funded by any source, besides your own personal funds?

Yes  No

### 9.4 \* Funding Status

You may select more than one answer.

- Applied For/Pending  
 Approved  
 Funding has Expired  
 Not Applicable (no outside funding in past, present, or future).

## 10.0 Study Funding II

10.1 \* Granting Agency or Commercial Sponsor Identify all sources of funding for this project. You can select more than one. There must be at least one checkbox selected for each agency/sponsor.

SKIP this question if you have not applied for outside funding.

	Sponsor	Funding	Protocol Control	Data Coordination	Monitoring	Auditing	Pass Through Funding
Personal							
Federal - NIH							
Pharmaceutical							
Private - Non-profit	Meriter Foundation						
State Government							

Local Government								
Federal - Other								
Business - Profit								
UW Madison/UW Hospital and Clinics								

**10.2 \* Is the sponsor, a commercial sponsor?**

- Yes
- No - my study is grant funded.
- I have no sponsor or outside funding for my study.

**10.3 Study Budget**

If you are anticipating outside funding for this research, you will need to submit your study budget. You'll upload your study budget later in the Intial Review Submission Packet in the Other Study Documents section.

**11.0 Locations**

**11.1 Where is the research being conducted?**

- UPH - Meriter Entities**
- UnityPoint Health - Meriter hospital
  - UnityPoint at Home (formerly Meriter Home Health)
  - UnityPoint Health - Meriter - Labarotories
  - UnityPoint Health - Meriter clinics
  - Other UnityPoint Health - Meriter Entity
- Entities Outside of UPH - Meriter**
- University of Wisconsin Hospital & Clinics (UWHC)
  - Other
- If you checked one of the OTHER boxes please explain.**

**12.0 Research Design & Procedures**

**12.1 \* Please list all departments, nursing units, etc. that will be involved at Meriter Hospital (e.g. blood bank, 6 North nursing unit, etc.). Enter the name of the person your study team has been in contact with for each area. Read the HELP Bubble in the right panel for more information.**

Department / Nursing Unit	Contact Person
7N, Neonatal ICU	[name] and [name]

**12.2 PURPOSE** What is the objective or purpose of your study? If you have specific aims, list them here. At the end of each paragraph hit Enter. Then hit Shift + Enter.

Specific Aim 1: To determine if a reduction in renal NIRS in preterm neonates correlates with current markers of neonatal AKI (decreased urine output or increased serum creatinine) in the first 7 days after birth.

Specific Aim 2: To determine if there is a significant reduction or increase in renal NIRS due to the use of medications in the NICU.

12.3 BACKGROUND What prior information or knowledge exists to support the conduct of this project or study? At the end of each paragraph hit Enter. Then hit Shift + Enter.

Preterm birth (< 37 weeks gestation) currently occurs in 1 in 8 deliveries and the majority of these infants are born with a low birth weight (LBW; <2.5kg), with many having a very low birth weight (VLBW; <1.5 kg). Although LBW is a well recognized risk factor for developing chronic kidney disease (CKD), prematurity and VLBW status have only recently been shown to be associated with later onset CKD. Children born preterm or with a VLBW are most at risk for developing CKD due to incomplete nephrogenesis, neonatal nephrotoxin exposures, and acute kidney injury (AKI) secondary to complex neonatal intensive care unit (NICU) hospitalizations. In 2013, Wisconsin had over 5,000 babies born preterm- over 600 of which were born with a VLBW. If you combine VLBW and LBW babies, the number of children at risk for developing CKD born each year in Wisconsin is over 1200.

Chronic kidney disease is a widespread public health epidemic associated with increased risks of cardiovascular disease and death. In Wisconsin, CKD has increased 3 fold since 1982 with early stage CKD now affecting over 40,000 and late stage CKD affecting over 3,000 in the state. Along with the rising incidence of CKD there have been associated increased costs – since 1993 the costs of caring for patients with CKD have increased 5 fold nationally. **The long-term goal of my research is to evaluate the contribution of preterm birth, NICU exposures and specifically AKI to the development of CKD in childhood and adulthood.** This past year I published a paper comparing the renal function of former preterm infants at 5 years of age. In this research study we found that preterm patients with a history of AKI in the NICU were 4 times as likely to have signs of CKD compared to those without a history of AKI in the NICU. This was consistent with pediatric and adult literature that has shown increased risk of CKD following an episode of AKI. It is clear from these studies that AKI is a significant risk factor for development of CKD and prevention of AKI should be a focus of all intensive care unit patients.

Acute kidney injury in the NICU is not only associated with long term development of CKD, but also with acute morbidity and increased rates of mortality. With AKI occurring in 12 to 40% of preterm infants, it is a common occurrence, particularly in the smallest and most preterm patients. The diagnosis of AKI in the NICU is currently based off of a standardized definition of increases in serum creatinine or decreases in urine output. Unfortunately, each of these criteria generally change hours to days after the initial insult resulting in the AKI band changes in therapy are generally not made until after the diagnosis. Multiple studies have examined the use of urinary biomarkers to diagnose AKI and many of these are promising for early detection of AKI- but these also are most often seen after the kidney injury. Ideally changes in blood flow or oxygenation of the kidneys could be detected prior to injury and this would allow clinicians to change therapy immediately.

Recently there has been increased use of a device to detect tissue oxygenation. Near infrared spectroscopy (NIRS) is a non-invasive skin-monitoring device used on patients to determine regional tissue oxygenation. Sensors can be placed in multiple locations, but most commonly the head, abdomen or flank are used to reflect brain, gut and kidney oxygen levels respectively. Studies in animals, pediatric and adult patients have shown that NIRS can be used to detect flow-induced changes in oxygen levels in the kidneys. In preterm neonates, a recent study showed that renal NIRS can be used to diagnose a hemodynamically significant PDA, a risk factor for AKI in nearly all neonatal AKI studies. In term neonates renal NIRS has been used in intra and post-operative cardiac surgery patients to detect AKI and has correlated with changes in both serum creatinine and urinary biomarkers. However, no studies currently exist demonstrating the correlation with urinary output or serum creatinine (the markers used for the current definition of AKI) and NIRS monitoring in preterm infants.

NIRS monitoring has been shown to be safe in multiple preterm studies. The sensor is both a light source and a detector used to measure the absorption of light by oxygenated and deoxygenated hemoglobin in the tissue. The sensor generates no heat and lasts between 1-4 days before needing to be changed. Normal renal NIRS values have been demonstrated in a number of small cohort studies and there are a number of factors that can affect the normal values: gestational age, post-menstrual age and hemoglobin. Given the large inter-individual variability, several different definitions have been used to define a low renal NIRS value: < 25% baseline, > 15 points below baseline and < 65%.

Given that AKI is common in preterm infants, can lead to long-term CKD, and current methods of diagnosis occur after injury, we propose that NIRS monitors can identify AKI in real time that may result in decreased rates of AKI and improved long-term outcomes.

12.4 ENROLLMENT Describe how subjects will be identified, and enrolled in the study. Indicate if randomization occurs and/or how subjects are assigned to study arms or groups if applicable. At the end of each paragraph hit Enter. Then hit Shift + Enter.

Goal Enrollment: 60 preterm patients

Eligibility: All preterm infants < 32 weeks admitted to Meriter UPH NICU

Inclusion Criteria:

1. Preterm neonate < 32 weeks
2. Admission to Meriter UPH NICU < 48 hours of age
3. Application of NIRS < 48 hours of age (Rationale: The most rapid change in renal function is in the first week of life. In the first 72 hours the serum creatinine is changing rapidly, reflecting a significant change in renal blood flow. Previous AKI studies have shown that 75-80% of AKI in the NICU occurs in the first week of life. In order to potentially capture this AKI episode we will aim to have NIRS on patients as early as possible, but for sure before 48 hours of age. If we started after 48 hours of age we may have potentially already missed the period of AKI and the renal NIRS may reflect post AKI oxygenation instead of oxygenation during the time of injury.)

Exclusion Criteria

1. Congenital anomaly of the Kidney or Urinary Tract (CAKUT)

Identification of Eligible Infants:

Each morning the RN Shift Manager will view the NICU census and identify subjects meeting inclusion criteria for the study. The PI, [name], will also check the NICU census daily to identify subjects which meet the inclusion criteria.

12.5 PROCEDURES Describe the study procedures or interventions that will be done at Meriter. If other institutions are involved, indicate how Meriter's involvement compares to the other institutions' involved. At the end of each paragraph hit Enter. Then hit Shift + Enter.

Solicitation of Study Interest

- Once a possible subject is identified, a member of the NICU team caring for the infant (NICU attending, NICU Fellow, NICU advanced practice provider, RN shift manager, or patient's RN) will speak with family to determine interest in participating in the study. If interest is identified, the PI or a NICU fellow will be notified to begin the consent process.

Solicitation of Informed Consent

- Once an interested family has been identified, the PI or NICU fellow will begin the informed consent process.

**Step One:** The Investigator (or IRB approved designee) will explain the study to the potential subject's parent verbally, providing all pertinent information (purpose, procedures, risks, benefits, alternatives to participation, etc.), and will allow the potential subject's parent ample opportunity to ask questions.

**Step Two:** Following this verbal explanation, the potential subject's parent will be provided with a written consent form and afforded up to 48 hours to consider whether or not to participate in the research.

**Step Three:** After allowing the potential subject's parent time to read the consent form, an Investigator listed on the consent form will meet with the potential subject's parent and answer any additional questions s/he may have.

- If the parent of the subject wishes to enroll the subject, a consent form will be signed, copied and given to the family for their records.

- If the consenting adult is a legal guardian or a minor parent, written proof (court document) will be required.

Application of Probe

- Application of regional NIRS neonatal probe (FDA approved for preterm infants) on top of a piece of Mepitel (gel impregnated gauze) barrier to the right or posterior flank above the iliac crest and below the costal margin (T10-L2) for monitoring or Renal sat (Rsat) levels within 48 hours of birth by one of the NICU

shift manager RNs.

- Application of regional NIRS neonatal probe to the central forehead for measurement of cerebral saturation (Csat) by one of the NICU shift manager RNs.

(Rationale for having shift manager RN's place mepitel and sensor: this small group of shift manager RNs will be trained to appropriately place the sensor and they are the skin experts for the NICU. They have the most expertise in applying skin protectants like mepitel and also have expertise in applying skin monitors and sensors like neonatal EKG probes and pulse oximeters which are similar to the neonatal NIRS probes to be used in this study)

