#### Measurement of Rsat and Csat

- Rsat and Csat levels will be measured continuously for the first 7 days of age
- Sensors will be used for as long as a value returns without signal degradation (average 4 days)
- Clinicians will be blinded to the saturation values

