#### Record Review

- Medical records will be reviewed for neonatal, perinatal, and maternal demographics. Vital sign information, labs, medications and imaging results will also be recorded. This data will be used to correlate NIRS values to a variety of perinatal and neonatal factors: vitals, labs, medications, hospitalization events, imaging studies. This data will hopefully inform future research on possible interventions to improve NIRS values in subsequent populations of preterm neonates.

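### Aim 2 asks what medications do to renal NIRS, but the only stated method is a correlation with no pre-dose comparison or adjustment, which could credit a drug with the effect of the illness it treats

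*Combined protocol and SAP*

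**What the plan says.** Section 12.2 lists two specific aims. The second is "To determine if there is a significant reduction or increase in renal NIRS due to the use of medications in the NICU".

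Exposure comes from chart review. Under Record Review in section 12.5, "Vital sign information, labs, medications and imaging results will also be recorded". The one sentence there that says how they will be analysed is: "This data will be used to correlate NIRS values to a variety of perinatal and neonatal factors: vitals, labs, medications, hospitalization events, imaging studies". Its stated purpose is modest: "This data will hopefully inform future research on possible interventions to improve NIRS values in subsequent populations of preterm neonates".

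Section 12.3 describes what else moves the measurement. It reports that "renal NIRS can be used to diagnose a hemodynamically significant PDA, a risk factor for AKI in nearly all neonatal AKI studies", and that "there are a number of factors that can affect the normal values: gestational age, post-menstrual age and hemoglobin".

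On measurement, section 12.5 says that "Rsat and Csat levels will be measured continuously for the first 7 days of age" and that "Clinicians will be blinded to the saturation values".

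Section 15.6, which asks for the statistical analysis, deals only with AKI versus no AKI. For Aim 2 the protocol names no drug, comparator, exposure window, contrast around dosing, covariate or method for repeated measurements.

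**The concern.** The aim asks for an effect, and the method yields an association. Infants receive drugs because of their condition, and the protocol itself says that some of those conditions, and the infant's maturity, are related to renal NIRS. Treated infants may therefore differ in renal saturation before the first dose. A correlation without a pre-dose comparison or adjustment would fold that difference into the apparent drug effect.

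At stake is one of the two specific aims. A drug that does nothing could be reported as changing renal oxygenation, and that result could then steer the choice of later studies. Aim 1 is not affected.

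**Working it through.** The plan gives no figure for Aim 2, so there is nothing to reproduce. The calculations below are illustrations of how large the bias could be.

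**Inputs from section 15.6:** 60 infants; mean renal NIRS 60 with AKI and 70 without, a 10-point difference; SD 10 in each group; 15% AKI, that is 9 of 60; alpha 5%.

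**Assumptions:** the drug has no effect; n infants are treated, with n from 10 to 30; treated and untreated infants are compared with a two-sided t-test on 58 degrees of freedom (critical value 2.002). The protocol does not state sidedness.

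**Formula:** for a pre-existing gap d, SE = 10 × √(1/n + 1/(60 − n)) and δ = d/SE. The probability of a false finding is the chance that a noncentral t with parameter δ falls outside ±2.002.

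**1. A 5-point gap (assumed)**

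| Treated n | SE | δ = 5/SE | False finding |
|---|---|---|---|
| 10 | 3.46 | 1.44 | 0.295 |
| 15 | 2.98 | 1.68 | 0.378 |
| 20 | 2.74 | 1.83 | 0.435 |
| 30 | 2.58 | 1.94 | 0.478 |

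**2. A gap that comes only from the expected AKI infants.** Suppose all 9 carry the 10-point deficit and all 9 are treated. The treated mean is then lower by 9 × 10/n.

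| Treated n | Gap = 90/n | δ | False finding |
|---|---|---|---|
| 10 | 9.0 | 2.60 | 0.72 |
| 15 | 6.0 | 2.01 | 0.51 |
| 20 | 4.5 | 1.64 | 0.37 |
| 30 | 3.0 | 1.16 | 0.21 |

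These are ceilings for this source of confounding, because every ill infant is treated.

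**3. Looser links between illness and prescribing.** Let 15% be ill, with a 10-point deficit, and let the drug go to a share a of ill infants and b of well infants. The ill fraction is 0.15a/(0.15a + 0.85b) among the treated and 0.15(1 − a)/[0.15(1 − a) + 0.85(1 − b)] among the untreated. The gap is 10 times the difference between these fractions. The overall SD is √(100 + 100 × 0.15 × 0.85) = 10.6.

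For a = 0.8 and b = 0.1, the fractions are 0.120/0.205 = 0.585 and 0.030/0.795 = 0.038. The gap is 5.5 points with 60 × 0.205 = 12.3 treated.

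| a | b | Gap | False finding |
|---|---|---|---|
| 0.3 | 0.3 | 0 | 5% |
| 0.5 | 0.3 | 1.2 | 7% |
| 0.8 | 0.3 | 2.7 | 16% |
| 0.8 | 0.1 | 5.5 | 35% |
| 0.9 | 0.05 | 7.4 | 53% |

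The bias runs from nothing to large, depending on how closely prescribing tracks illness. The documents do not say how closely it does.

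**The case against.** The strongest reply is that the protocol never commits to a crude comparison of treated with untreated infants. The Record Review sentence does not say whether the correlation is between or within infants. Aim 2 speaks of a reduction or increase, saturation is recorded continuously, and section 12.3 cites definitions of low NIRS relative to baseline. A within-infant analysis is open to the investigator. This stands: a reader might infer that the plan prescribes a comparison across infants and must give a biased answer, and the text does not support that. But the plan does not require the within-infant analysis either, so the choice could be made after the data are seen.

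A reader might also apply the plan's 10-point AKI contrast directly to treated versus untreated infants. That gives false findings in 81% to 97% of studies with 10 to 30 treated. The documents do not support this, because only 9 infants are expected to have AKI. With 30 treated, a 10-point gap would need all 30 treated infants, and no untreated infant, to carry the full deficit. PDA might be more common than AKI, but the documents give neither its rate nor its effect on NIRS.

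Two further points soften the concern without removing it. Clinicians cannot see the readings, so prescribing cannot respond to them, but it can still respond to the illness. The stated use of the correlations is to inform further research, which suits an association, whereas the aim is worded as an effect.

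**Conclusion.** The concern holds in this form: Aim 2 is causal, its only stated method is an unadjusted correlation with chart-recorded drugs, and the protocol itself names factors that could confound it. The analysis as described cannot support a conclusion that a change is caused by a drug. It *could* attribute illness to treatment. That it *would* do so is not shown, since the size and direction of the bias depend on prescribing.

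Under the stated assumptions (no drug effect, SD 10, 60 infants, 10 to 30 treated, two-sided 5% test), a 5-point prior gap produces a false effect in about 30% to 48% of studies. The 5 points are an assumption, not a figure from the plan. If the expected AKI infants are the only source, the ceilings run from 72% with 10 treated to 21% with 30. Looser prescribing brings the rate down towards 5%.

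This is a worthwhile and inexpensive improvement to a secondary part of the study.

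**What to change.** - Reword Aim 2 so that it asks about change in renal NIRS *after* a medication, or change *associated with* it.
- Name the drug classes to be studied.
- Make the analysis a within-infant comparison of renal saturation in fixed windows before and after the first dose. Use a linear mixed model with a random infant intercept and terms for postnatal age, hemoglobin and, where charted, the indication or illness severity (for example PDA status).
- State the limit. This contrast removes stable differences between infants, but not confounding by illness that changes around the time of dosing.

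The cost is protocol wording and modest analysis work, with no added infants or procedures, and there are two downsides. First, the protocol says that medications are recorded but does not mention dose times. The data form required in section 14.1 is not among the documents, so the investigator should confirm that times are abstracted. Second, the sensor may be applied as late as 48 hours of age (section 12.4). Infants started on a drug before application contribute no pre-dose window, and the documents do not show how many that would be.
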